4.3 Life Style Guidelines

Patients who are biologically capable of having children and sexually active must agree to use an acceptable method of contraception for the duration of the treatment period and for at least 6 months after the last dose of study treatment. The Investigator will counsel the patient on selection of contraception method and instruct the patient in its consistent and correct use. Examples of acceptable forms of contraception include:

1. Oral, inserted, injected or implanted hormonal methods of contraception, provided it has been used for an adequate period of time to ensure effectiveness.
2. Correctly placed copper containing intrauterine device (IUD).
3. Male condom or female condom used WITH a spermicide.
4. Male sterilization with confirmed absence of sperm in the post-vasectomy ejaculate.
5. Bilateral tubal ligation or bilateral salpingectomy.

The Investigator will instruct the patient to call immediately if the selected birth control method is discontinued or if pregnancy is known or suspected.

Note: Women are considered post-menopausal and/or not of child bearing potential if they have had 12 months of natural (spontaneous) amenorrhea with an appropriate clinical profile (e.g., age appropriate, history of vasomotor symptoms) or have had surgical bilateral oophorectomy (with or without hysterectomy) or tubal ligation at least 6 months ago. In case of any ambiguity, the reproductive status of the woman should be confirmed by hormone level assessment.

4.4 Enrollment into Study

Following completion of the study-specific informed consent process and review of all screening procedures, patient eligibility will be confirmed by appropriately qualified staff at the investigational site. Patients will be enrolled by entry into a patient registration log provided by the Sponsor and maintained by the study site, and completion of the patient registration procedure detailed in the Study Manual. Each patient will be assigned a sequential number by the study site. The patient number must be used on all documentation and correspondence with the Sponsor, Contract Research Organization (CRO) and laboratory vendors.

5 STUDY TREATMENTS

5.1 Sitravatinib

5.1.1 Formulation, Packaging and Storage

This study began patient treatment with the sitravatinib free base capsule formulation used in previous clinical trials. Cohorts 1 through 6 will continue to receive the free base formulation. For Cohorts 7 through 10, transition to use of an alternative formulation, sitravatinib malate capsule formulation, is being implemented with protocol Version 4.0. Newly enrolled patients in Cohorts 7 through 10 will receive the malate capsule formulation. Patients on study treatment with the free base capsule formulation at the time the malate capsule formulation is introduced will remain on the free base capsule formulation until treatment discontinuation. The formulations are described below.

- The composition of the drug product used in previous clinical trials consists of a blend of sitravatinib (MGCD516) free base drug substance, microcrystalline cellulose, polysorbate 80, and colloidal silicon dioxide. The blend is filled into hard gelatin capsules. To help differentiate between the products, the free base formulation will be labeled with the drug product code “MGCD516”.
- The sitravatinib malate capsule product consists of a blend of sitravatinib malate drug substance, microcrystalline cellulose, mannitol, croscarmellose sodium, colloidal silicon dioxide, and magnesium stearate; the blend is filled into hard gelatin capsules. To help differentiate between the products, the malate formulation will be labeled with the drug product name “Sitravatinib”.

The strengths of all sitravatinib capsule formulations are expressed based on sitravatinib free base weight. Dose strengths of sitravatinib and additional packaging differences between formulations will be provided in the Pharmacy Study Manual.

Sitravatinib drug product is packaged in high-density polyethylene (HDPE), white opaque, round 60 cc bottles. A tamper-proof heat induction seal and a child-resistant closure are used. The provided bottles may be labeled for specific patient use and given to the patient.

Sitravatinib medication labels comply with the legal requirements of the United States.

Investigational clinical trial material should be stored in an area that is secure, with limited access and monitored for temperature using a calibrated thermostat or thermometer. Sitravatinib capsules should be stored under the conditions stated on the container labels and the Pharmacy Study Manual.

Refer to the Pharmacy Study Manual for details.

5.1.2 Preparation, Dispensing, Administration and Accountability

Only qualified personnel who are familiar with procedures that minimize undue exposure to them and to the environment should undertake the preparation, handling, and safe disposal of chemotherapeutic agents.

Study site personnel will dispense bottles containing sitravatinib capsules on Day 1 of each treatment cycle. Sufficient supply will be provided for each cycle and extra capsules may be provided to cover additional days in case of delayed clinic visits or lost capsules. Study capsules will be dispensed in HDPE bottles provided by the Sponsor.

Sitravatinib capsules will be administered orally, once daily (QD), in a continuous regimen expressed in 28-day cycles for the sitravatinib and nivolumab combination cohorts and in 21-day cycles for the sitravatinib, pembrolizumab and enfortumab combination cohorts.

- For all patients in Cohorts 1 through 6, the starting dose using the free base formulation is 120 mg QD.
- For newly enrolled patients in Cohorts 7 and 8, the starting dose using the malate capsule formulation is 100 mg QD. The starting dose using the free base capsule formulation (for patients who began treatment on free base capsule formulation at the time the malate capsule formulation is introduced) is 120 mg QD.
- For the sitravatinib, pembrolizumab and enfortumab combination cohorts, the sitravatinib starting dose for the lead-in dose escalation portion of Cohort 9 using the malate capsule formulation will be 35 mg QD which represents three dose levels below the dose administered as a single agent and in combination (with nivolumab) Phase 2 and Phase 3 trials. If a dose is identified for sitravatinib in combination with pembrolizumab and enfortumab, this recommended starting dose will be used for subsequent contingent sitravatinib, pembrolizumab and enfortumab combination cohorts (dose expansion portion of Cohort 9 and Cohort 10).

Depending on safety observations, the sitravatinib dose during treatment may be reduced in accordance with [Table 5](#) for patients administered the free base capsule formulation and in accordance with [Table 6](#) for patients administered the malate capsule formulation.

The following guidelines should be followed for sitravatinib administration:

- Dosing in the morning is preferred.
- Capsules should be taken on an empty stomach (at least 2-hour fast before each dose and no food for a minimum of 1 hour after each dose). The fasting requirement may be eliminated based on the outcome of an ongoing food-effect study under a separate study protocol. Any change in fasting will be implemented

by Administrative Letter to Investigators and reiterated in the next protocol amendment required within the study.

- Capsules should be taken with at least 200 mL (~1 cup) of water.
- Patients should swallow the capsules whole and not chew them.
- If vomiting occurs after dosing, sitravatinib doses should not be replaced.

On days when nivolumab, pembrolizumab or enfortumab are administered, the daily dose of sitravatinib should precede the nivolumab, pembrolizumab or enfortumab infusion for logistical reasons. This order of dosing is of particular interest on days when blood sampling is scheduled for sitravatinib PK.

All sitravatinib study treatment supplies will be accounted for in the drug accountability inventory forms supplied by the Sponsor or using locally approved forms that include all required information. The drug accountability inventory forms must identify the study drug, including batch or lot numbers and account for its disposition on a patient-by-patient basis, including specific dates and quantities. The forms must be signed by the individual who dispensed the drug.

Patients will be asked to record their daily dosing on Sponsor provided diary cards and report any missed doses or lost doses at the next clinic visit. On the back of each Sponsor provided diary card, written dosing instructions for sitravatinib capsules are provided (e.g., fasting instructions, take with water, etc.). Patients should be told to bring study treatment bottle(s) (empty or not) and completed dosing diaries with them to the clinic visit for a compliance check and capsule count. Study site personnel will retain the bottle(s) until a monitor has completed reconciliation and retain dosing diaries with site study files.

At the end of the study, all unused sitravatinib drug supplies must be destroyed in accordance with local Standard Operating Procedure provided to the Sponsor for the Trial Master File, or returned to the Sponsor or its appointed agent, as directed by the Sponsor.

5.1.3 Sitravatinib Dose Modification and Discontinuation

This protocol provides guidance for dose modification of sitravatinib (i.e., interruption, dose reduction or discontinuation) for AEs attributed to sitravatinib. For adverse events attributed to nivolumab, pembrolizumab or enfortumab see the current [OPDIVO US Prescribing Information](#), [KEYTRUDA US Prescribing Information](#) and [PADCEV US Prescribing Information](#), Section 5.2.4 for dose nivolumab modifications, Section 5.3.4 for dose for pembrolizumab modifications, and Section 5.4.4 for dose for enfortumab modifications.

Available dose levels for each of the sitravatinib formulations are outlined in [Table 5](#) and [Table 6](#). Dose modifications guidelines for the malate capsule formulation ([Table 6](#))

follow comparable dose reduction proportions used for the free base capsule formulation. Guidelines for sitravatinib dose modifications to be implemented to manage adverse events are described in Section 5.3.1 and 5.3.3. Once the dose has been reduced, re-escalation is generally not recommended but may be considered on a case-by-case basis with approval from the Medical Monitor. If the administration of sitravatinib is interrupted for reasons other than toxicity, then treatment with the study drug may be resumed at the same dose.

The starting dose for sitravatinib using the free base capsule formulation is 120 mg QD.

Table 5: Sitravatinib Sequential Dose Reductions for Individual Patients on Free Base Capsule Formulation

120 mg once daily
80 mg once daily
60 mg once daily
40 mg once daily

The starting dose for sitravatinib using the malate capsule formulation is 100 mg QD.

Table 6: Sitravatinib Sequential Dose Reductions for Individual Patients on Malate Capsule Formulation

100 mg once daily
70 mg once daily
50 mg once daily
35 mg once daily
20 mg once daily*

* This dose level is only available for Cohorts 9 and 10.

In the event of sitravatinib-related AE, dose reduction with continuous treatment is preferred over repeated dose interruption. If treatment with sitravatinib is delayed for ≥ 14 days, then resumption at a reduced dose should be considered. If treatment with sitravatinib is withheld for ≥ 28 consecutive days, then permanent discontinuation of sitravatinib should be considered. If one study drug is interrupted or discontinued, administration of the other study drug may continue at the discretion of the Investigator.

5.2 Nivolumab Study Drug

Nivolumab will be obtained from commercial sources and managed in accordance with the [OPDIVO US Prescribing Information](#). The following reports information and guidance included in the OPDIVO US Prescribing Information dated June 2020. Refer the current OPDIVO US Prescribing Information provided by the manufacturer for updates during the conduct of this clinical trial.

5.2.1 Formulation and Packaging

Refer to the current OPDIVO US Prescribing Information.

5.2.2 Preparation and Dispensing

Refer to the current OPDIVO US Prescribing Information.

5.2.3 Administration

Nivolumab (OPDIVO) will be administered in this study as an intravenous infusion over approximately 30 minutes (+/- 5 minutes) at 240 mg every 2 weeks (Q2W) or 480 mg every 4 weeks (Q4W), at the discretion of the Investigator and in accordance with the current [OPDIVO US Prescribing Information](#). Note: nivolumab should be administered after sitravatinib (and specifically after the 30 minute PK sampling on applicable study visits).

5.2.4 Nivolumab Dose Modification

Required dose modifications (i.e., interruption or discontinuation) for nivolumab should be performed per the current [OPDIVO US Prescribing Information](#), in addition to potential dose modifications for sitravatinib in accordance to Section 5.1.3.

If one agent is interrupted or discontinued, administration of the other agent may continue at the discretion of the Investigator.

Change from OPDIVO US Prescribing Information for This Study

One change from the Prescribing Information will be implemented in this study. This protocol allows enrollment of patients having a limited degree of renal impairment. For this reason, the guidance for management of patients who experience nephritis and renal dysfunction that is not thought to be immune-mediated will be adjusted. The Prescribing Information indicates that dosing should be withheld in the event of serum creatinine more than 1.5 and up to 6 times the upper limit of normal and discontinued permanently if more than 6 times the upper limit of normal.

In this study, the baseline (screening) value will substitute for the upper limit of normal. Nivolumab dosing should be withheld if the serum creatinine increases to more than 1.5 and up to 6 times the baseline (screening) value and discontinued permanently if more than 6 times the baseline (screening) value.

5.3 Pembrolizumab Study Drug

Pembrolizumab will be obtained from commercial sources and managed in accordance with the [KEYTRUDA US Prescribing Information](#). The following reports information and guidance included in the [KEYTRUDA US Prescribing Information](#) dated April 2020.

Refer to the current [KEYTRUDA US Prescribing Information](#) provided by the manufacturer for updates during the conduct of this clinical trial.

5.3.1 Formulation and Packaging

Refer to the current [KEYTRUDA US Prescribing Information](#).

5.3.2 Preparation and Dispensing

Refer to the current [KEYTRUDA US Prescribing Information](#).

5.3.3 Administration

Pembrolizumab (KEYTRUDA) will be administered in this study as an intravenous infusion over approximately 30 minutes (+/- 5 minutes) at 200 mg every 3 weeks (Q3W), in accordance with the current [KEYTRUDA US Prescribing Information](#). Note: pembrolizumab should be administered after sitravatinib (and specifically after the 30 minute PK sampling on applicable study visits), and at least 30 minutes before enfortumab.

5.3.4 Pembrolizumab Dose Modification

Required dose modifications (i.e., interruption or discontinuation) for pembrolizumab should be performed per the current [KEYTRUDA US Prescribing Information](#), in addition to potential dose modifications for sitravatinib in accordance to Section 5.1.3 and dose modifications for enfortumab per the current [PADCEV US Prescribing Information](#) in Section 5.4.4.

If one agent is interrupted or discontinued, administration of the other agent may continue at the discretion of the Investigator.

5.4 Enfortumab Study Drug

Enfortumab will be obtained from commercial sources and managed in accordance with the [PADCEV US Prescribing Information](#). The following reports information and guidance included in the [PADCEV US Prescribing Information](#) dated December 2019. Refer the current [PADCEV US Prescribing Information](#) provided by the manufacturer for updates during the conduct of this clinical trial.

5.4.1 Formulation and Packaging

Refer to the current [PADCEV US Prescribing Information](#).

5.4.2 Preparation and Dispensing

Refer the current [PADCEV US Prescribing Information](#).

5.4.3 Administration

Dosing is based on patient weight. Enfortumab will be administered at mg/kg doses based on the patient's actual body weight at Cycle 1 Day 1. For on-study dosing, the dose must be adjusted if the patient's weight changes by $\geq 10\%$ from their Cycle 1 Day 1 weight, or if enfortumab dose modification criteria (see Section 5.4.4) are met. Other dose adjustments for changes in body weight $<10\%$ are permitted per institutional standard. For patients who weigh > 100 kg, the dose will be calculated based on 100 kg weight. Institutional dose rounding rules may be applied to this protocol, but otherwise, doses of the investigational product will be rounded to the nearest milligram.

Enfortumab (PADCEV) will be administered in this study as an intravenous infusion over approximately 30 minutes (± 5 minutes) at the selected dose level (see Appendix 9) on Days 1, and 8 of a 21-day cycle, at the discretion of the Investigator and in accordance with the current [PADCEV US Prescribing Information](#). Note: enfortumab should be administered at least 30 minutes after pembrolizumab.

Patients will receive enfortumab administration only if their laboratory results of blood drawn within 24 hours prior to dosing meets the following study drug administration laboratory criteria:

- Blood glucose ≤ 250 mg/dL.

5.4.4 Enfortumab Dose Modification

Required dose modifications (i.e., interruption, dose reduction or discontinuation) for enfortumab should be performed per the current [PADCEV US Prescribing Information](#), in addition to potential dose modifications for sitravatinib in accordance to Section 5.1.3 and dose modifications for pembrolizumab per the current [KEYTRUDA US Prescribing Information](#) in Section 5.3.4. Available dose levels for enfortumab are outlined in Table 7.

Table 7: Enfortumab Sequential Dose Reductions for Individual Patients

1.25 mg/kg up to 125 mg
1.0 mg/kg up to 100 mg
0.75 mg/kg up to 75 mg
0.5 mg/kg up to 50 mg

If one agent is interrupted or discontinued, administration of the other agent may continue at the discretion of the Investigator.

5.5 Management of Adverse Events

5.5.1 Sitravatinib-Related Adverse Events

5.5.1.1 General Management of Non-Hematological Toxicities

In the event of symptomatic sitravatinib-related AEs, dose reduction to a level that can be administered continuously is preferred over continuing dosing until interruption becomes necessary. Symptomatic Grade 2 sitravatinib-related non-hematological AEs occurring any time on study, particularly early in treatment (e.g., Cycle 1 Day 15 or Cycle 2 Day 1), are recommended to be managed using dose reduction to the next lower dose level, per the reduction schedule outlined in [Table 5](#) (free base capsule formulation) and [Table 6](#) (malate capsule formulation), rather than treatment interruption.

Non-hematological toxicities \geq Grade 3 and considered to be related to sitravatinib treatment should be managed with sitravatinib interruption, with or without dose reduction, until resolution of toxicity to \leq Grade 1 or to baseline value. If the toxicity is adequately managed by routine supportive care (such as electrolyte supplementation), or is a Grade 3 amylase or lipase elevation, treatment may be resumed at the same dose; if not, treatment may be resumed at a reduced dose as outlined in [Table 8](#). Recurrence of the toxicity may be managed similarly. If sitravatinib is interrupted for \geq 28 days, permanent discontinuation of sitravatinib should be considered.

Table 8: Sitravatinib Dose Modifications – Non-Hematological Drug-Related Toxicities¹

Toxicity	Treatment Delay	Dose Modification
Grade 1	Continue treatment unchanged	
Grade 2 Asymptomatic	May be implemented based on Investigator discretion ²	
Grade 2 Symptomatic	May be implemented based on Investigator discretion ² Dose reduction to the next lower dose level is recommended over treatment interruption	
Grade 3 or 4	Hold until \leq Grade 1 or return to baseline ²	Resume at dose level one or more levels below that inducing the toxicity. Exceptions presented in footnotes ^{2,3}

¹ Management of adverse events of interest for sitravatinib are presented in Section 5.5.1.3.

² The current [OPDIVO US Prescribing Information](#), [KEYTRUDA US Prescribing Information](#) and [PADCEV US Prescribing Information](#) must be consulted to determine appropriate dose modifications for nivolumab, pembrolizumab and enfortumab.

³ Patients may resume at the same dose in the following cases:

- Grade 3 or 4 electrolyte abnormality that is not clinically complicated and resolves spontaneously or with conventional medical treatment within 72 hours;
- Grade 3 or 4 amylase or lipase elevation that is not associated with symptoms or clinical manifestations of pancreatitis.

5.5.1.2 *General Management of Hematological Toxicities*

Hematological toxicities are not a frequent cause of treatment interruption or discontinuation of sitravatinib treatment. Observed \geq Grade 3 hematological events that are considered to be causally related to sitravatinib should initially be managed using treatment interruption. In addition, dose reduction of sitravatinib should be implemented in the following cases:

- Grade 3 or 4 febrile neutropenia;
- Grade 4 neutropenia persisting for \geq 8 days; or
- Grade 4 thrombocytopenia of any duration or Grade 3 thrombocytopenia with bleeding.

5.5.1.3 *Management of Selected Adverse Event*

The following are guidelines for management of potential adverse events more specific to treatment with sitravatinib or agents in the same class of cancer treatment.

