Increased lipase has been observed in patients treated with sitravatinib and other inhibitors of the VEGF pathway. Although the mechanism has not been fully elucidated, inhibition of VEGF may lead to acinar cell apoptosis resulting in the release of autodigestive enzymes (Sevin-2012). Most sitravatinib treatment-emergent events of increased amylase and lipase were asymptomatic while some were associated with signs and/or symptoms of pancreatitis. Treatment-related increased lipase has been observed in 10% of patients treated with sitravatinib monotherapy. Increased lipase is rare with pembrolizumab monotherapy, however it occurs in 18% (8/45) of urothelial carcinoma patients receiving the combination of pembrolizumab and enfortumab in Study EV-103 (Rosenberg-2020).

Finally, whereas sitravatinib administered in combination pembrolizumab and enfortumab is unlikely to result in drug-drug interactions (DDI), the only potential for DDIs stems from MMAE being an in vitro substrate of both CYP3A4 and P-glycoprotein (P-gp) (see below), and sitravatinib being an in vitro inhibitor of both CYP3A4 and P-gp (see Section 1.7.1.2). To mitigate the potential for increased MMAE exposure with the combination of sitravatinib, pembrolizumab and enfortumab and any subsequent clinical impact, the lead-in dose escalation evaluation (Cohort 9) of the combination will initiate with a sitravatinib starting dose representing three dose levels (~65%) below the dose administered as a single-agent and in combination with nivolumab in Phase 2 and Phase 3 trials. In addition, a dose de-escalation step for enfortumab may be undertaken as appropriate. Refer to [Appendix 9](#) for study design details of cohorts investigating the combination of sitravatinib, pembrolizumab and enfortumab.

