8.2 Adverse Events

An adverse event (AE) is any reaction, side effect or other undesirable medical event that occurs during participation in a clinical trial, regardless of treatment group or suspected causal relationship to study treatment. Assessment of adverse events will include type, incidence, severity (graded by the National Cancer Institute [NCI] Common Terminology Criteria for Adverse Events [CTCAE, Version 5.0]), timing, seriousness, and relatedness to study treatment. A treatment emergent AE (TEAE) is an AE that occurs after the first dose of any study treatment or any preexisting condition that increases in severity after the first dose of study treatment.

All observed or volunteered AEs will be recorded in source documents and reported in the CRF. The best available medical terminology should be used to describe AEs in source documents and CRFs. Terms describing the diagnosis are preferred over individual signs and symptoms of the diagnosis. If determination of the diagnosis is delayed, record signs and symptoms and add the diagnosis as an additional AE when available; follow all recorded AEs to resolution. The actual date of onset should be recorded in all cases. Ongoing AEs that change in attribution or severity should have the date of change entered as the “end date” and a new AE record should be opened with the changed details. Examples of AEs include but are not limited to:

- Signs or symptoms of co-morbidity, illness, or toxicity of study treatment;
- Signs or symptoms of worsening malignancy under study (disease progression assessed by measurement of malignant lesions should not be reported as an AE);
- Laboratory abnormalities (see Section 8.2.1 for guidance for reporting in CRF);
- Hypersensitivity;
- Drug abuse, dependency, overdose, withdrawal or misuse;
- Signs or symptoms of drug interactions;

- Extravasation;
- Exposure during pregnancy or via breastfeeding;
- Medication error; or
- Occupational exposure.

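### For a sitravatinib-related Grade 3 amylase or lipase elevation with pancreatitis symptoms, the Protocol Section 5.5.1.1 text permits a same-dose restart where Table 8 with footnote 3 directs a lower dose

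*Protocol*

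**What the plan says.** Section 5.5.1.1 of the protocol requires sitravatinib to be interrupted for a related non-hematological toxicity of Grade 3 or higher until it returns to Grade 1 or lower, or to baseline. The text then gives two routes back to the same dose. The first is general: "If the toxicity is adequately managed by routine supportive care (such as electrolyte supplementation"). The second is specific to pancreatic enzymes: "or is a Grade 3 amylase or lipase elevation, treatment may be resumed at the same dose". Any other toxicity may restart at a reduced dose, for which the text points to Table 8.

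Table 8 has the same hold for Grade 3 or 4, followed by "Resume at dose level one or more levels below that inducing the toxicity", subject to footnotes 2 and 3. Footnote 2 concerns only the partner drugs. Footnote 3 lists two cases that may restart at the same dose. One is an uncomplicated electrolyte disturbance of either grade that settles within 72 hours. The other concerns pancreatic enzymes and is worded as follows: "Grade 3 or 4 amylase or lipase elevation that is not associated with symptoms or clinical manifestations of pancreatitis".

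**The concern.** The footnote uses pancreatitis features (symptoms or clinical manifestations) to divide enzyme elevations that may restart at the same dose from those that may not. The text leaves that dividing line out. A site working from the text could put a patient back on the dose at which a Grade 3 elevation with pancreatitis features arose, while a site working from the table would go down a level. The supportive-care route opens the same door, because it carries no symptom condition and no grade limit.

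What is at stake is patient safety on re-exposure and consistent dosing across sites.

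**Working it through.** There is no planned figure to reproduce. The check sets the two rules side by side for sitravatinib-related elevations, after the hold that both require.

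| Elevation | Section 5.5.1.1 text | Table 8 with footnote 3 | Result |
|---|---|---|---|
| Grade 3, no pancreatitis features | Same dose permitted | Same dose permitted | Agree |
| Grade 3, with features | Same dose permitted | At least one level lower | Conflict |
| Grade 4, no features | Enzyme clause does not reach it; reduced dose unless supportive care suffices | Same dose permitted | Text narrower than table |
| Grade 4, with features | Reduced dose unless supportive care suffices | At least one level lower | Conflict only through the supportive-care route |

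**Does anything else decide row two?**

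- The text refers to Table 8 only for toxicities outside its own same-dose cases, so the table is not made controlling for a Grade 3 enzyme elevation.
- Section 5.1.3 states a preference: "In the event of sitravatinib-related AE, dose reduction with continuous treatment is preferred over repeated dose interruption". It compares reduction with interruption and does not withdraw the same-dose permission. For its adverse-event rules it points to Sections 5.3.1 and 5.3.3, which in this version cover pembrolizumab packaging and administration.
- Section 5.5.1.3, on selected adverse events, has no subsection on pancreatitis or lipase.
- Section 5.5.5 governs events judged immune-mediated. For Grade 3 and 4 it leaves the sitravatinib restart dose, same or lower, to the investigator. Those events are outside this point.

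**How many patients?** Section 1.3.3.2 reports treatment-related Grade 3 lipase increase, at 26 June 2019, as follows:

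- This study: 10% of 40 = 0.10 × 40 = 4 patients.
- All patients on sitravatinib plus nivolumab: 5% of 184. A rounded 5% covers 4.5% to 5.5%, that is 8.3 to 10.1, so 9 or 10 patients.

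Neither figure says how many had pancreatitis features, so the disputed lipase cases among the 4 could number anywhere from 0 to 4. Nor is 4 a firm ceiling on all disputed cases: no Grade 3 amylase count is given, and a case recorded as pancreatitis would not appear under lipase. The rates are also treatment-related, whereas the rule applies to sitravatinib-related toxicity.

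**How much dose?** One-level reduction = (current − next) / current.

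- Table 5, free base: (120 − 80)/120 = 33%; (80 − 60)/80 = 25%; (60 − 40)/60 = 33%.
- Table 6, malate: (100 − 70)/100 = 30%; (70 − 50)/70 = 29%; (50 − 35)/50 = 30%.

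The range for Cohorts 1 to 8 is therefore 25% to 33%. The further malate step, (35 − 20)/35 = 43%, is open only to Cohorts 9 and 10 and has little reach. The SAP's Figure 1 note says the Cohort 9 expansion and Cohort 10 will not be opened, and protocol Appendix 9 bars reductions during Cycle 1 of the Cohort 9 lead-in.

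**The case against.** The strongest reply is that the conflict has little practical bite. The text says the same dose may be used, so a site that always reduces breaks neither rule. The hold to Grade 1 or lower, or baseline, comes first under both. Section 5.5.1.1 itself opens by preferring dose reduction for symptomatic sitravatinib-related events. Section 8.2 adds that "Terms describing the diagnosis are preferred over individual signs and symptoms of the diagnosis", so a diagnosed pancreatitis may be recorded as such and leave the enzyme clause to laboratory-only findings.

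Most of this stands, and it limits the point. A reader might infer that the text requires the same dose, or that a patient would be restarted while the toxicity is still at Grade 3. Neither is supported. A reader might also take Section 1.7.2.2 as proof that the disputed event has occurred: "Most sitravatinib treatment-emergent events of increased amylase and lipase were asymptomatic while some were associated with signs and/or symptoms of pancreatitis". That sentence gives no grade, so it shows that elevations with symptoms occur but not that Grade 3 ones have.

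The reply does not remove the mismatch. The opening preference is set against dosing on until interruption becomes necessary, and is not a restart rule. Section 8.2 also provides for signs to be recorded first and a delayed diagnosis added as a further event. Footnote 3 itself treats elevations with pancreatitis features as a subset of amylase or lipase elevations, so the text's unqualified phrase covers them.

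A reader might go further and infer that the supportive-care route should be struck out for every toxicity because footnote 3 lists only two exceptions. The documents do not support that. Section 5.5.1.3.1 leaves the restart dose after Grade 3 hypertension to the investigator, and Section 5.5.1.3.3 allows restart once diarrhea is controlled without stating a reduction.

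**Conclusion.** The inconsistency is real and narrow. It concerns a sitravatinib-related Grade 3 amylase or lipase elevation with symptoms or clinical manifestations of pancreatitis, not judged immune-mediated, after the required hold. There the text permits a restart at a dose that Table 8 with footnote 3 rules out.

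The number of affected patients is unknown and may be zero. The nearest figure is 4 of 40 with treatment-related Grade 3 lipase increase, symptom status and amylase counts not stated. For an affected patient in Cohorts 1 to 8 who is above the lowest listed dose, the difference is 25% to 33% of dose. That assumes a one-level reduction; Table 8 also allows more. No endpoint, sample size, power or analysis is affected.

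The conclusion rests on the wording alone, and on reading footnote 3 as the sponsor's intended dividing line.

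**What to change.** In the Section 5.5.1.1 sentence, replace the Grade 3 amylase or lipase clause with the footnote 3 wording: "Grade 3 or 4 amylase or lipase elevation that is not associated with symptoms or clinical manifestations of pancreatitis". This also aligns the grades, since the footnote covers Grade 4 and the text does not. Add that the supportive-care clause does not apply to amylase or lipase elevations with such symptoms or manifestations. Leave the supportive-care route otherwise unchanged, and leave Section 5.5.5 as it is.

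The drafting is one clause and one short sentence. Under Section 13.1 the change needs an Administrative Letter or an amendment, with submission to and approval by the IRB/EC/REB before sites apply it. The SAP needs no change.
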